### **6.3 Follow-Up and Record of Events**

- The patients should be followed-up for up to 2 years.
- The incidence of late toxicities  $>$  grade 3 by Common Toxicity Criteria for Adverse Events version 4.0 (NCI-CTCAE v.4) should be recorded.
- All causes of death (if occur) will be recorded. Deaths due to unknown cause are counted as deaths due to NPC if disease is still present at last assessment.

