Enrolled subjects were predominantly of Asian ethnicity (82%), male (77.8%), with an Eastern Cooperative Oncology Group (ECOG) performance status of 1-2 (62%). Again, the enrolled subjects are heavily pre-treated with approximately 60% had received 3 or more prior treatments for metastatic disease. A total of 44 patients were evaluated and the overall ORR was 20.5% (CR = 1; PR= 8). Nine patients received nivolumab for  $\geq$ 12 months (20%). The 1-year OS rate was 59% and 1-year PFS rate was 19.3%. Treatment was well tolerated and 22.2% of subjects experienced  $\geq$  grade 3 drug-related adverse events.

Collectively, anti-PD1 therapy has promising activity in R/M NPC and manageable toxicity profile. The overall survival rate was compared favorably with historical data in similar populations. PD-L1 is a potential predictive biomarker of efficacy.

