# 3 ELIGIBILITY CRITERIA

## 3.1 Inclusion Criteria

[figure not shown]
1. Histologically or cytologically confirmed non-keratinizing differentiated (World Health Organization WHO Type II) or undifferentiated (WHO Type III) nasopharyngeal carcinoma (NPC) that has recurred at regional or / and distant sites
2. Measurable disease according to the RECIST criteria (version 1.1) for the evaluation of measurable disease
3. Received one or more lines of chemotherapy, which must include prior treatment with a platinum agent either
  - a. For the treatment of metastatic or recurrent disease
  - b. Experienced progression of disease within 6 months following completion of a platinum-based combination therapy as part of (neo)-adjuvant therapy
4. Male or female subjects with age: 18-79 years old
5. Eastern Cooperative Oncology Group (ECOG) performance status of 0, 1 or 2
6. No prior immunotherapy
7. Written informed consent obtained for clinical trial participation and providing archival tumor tissue, if available
8. Females of childbearing potential or non-sterilized male who are sexually active must use a highly effective method of contraception
9. Females of childbearing potential must have negative serum or urine pregnancy test
10. Have life expectancy  $\geq 3$  months
11. Adequate organ function as defined as:
  - a. Absolute neutrophil count  $\geq 1.5 \times 10^9/L$
  - b. Platelet count  $\geq 100 \times 10^9/L$
  - c. Hemoglobin  $\geq 8.0 \text{ g/dL}$
  - d. Serum alanine aminotransferase ([ALT]; serum glutamate-pyruvate transferase [SGPT]), or serum aspartate aminotransferase [AST] where available at the center)  $< 2.5 \times$  upper limit of normal (ULN), OR  $< 5 \times$  ULN in the presence of liver metastases
  - e. Serum total bilirubin  $< 2 \times$  ULN
  - f. Serum creatinine  $< 1.5 \times$  ULN

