## 6.2 Outcome Measures

Primary outcome:

- Objective response rate (ORR): The percentage of patients with radiologically complete or partial response as determined by the Investigator according to RECIST version 1.1.

Secondary outcomes:

- Progression-free Survival (PFS): PFS is measured from the date of informed consent to radiographically documented progression according to RECIST 1.1 or death from any cause (whichever occurs first). Participants alive and without disease progression or lost to follow-up will be censored at the date of their last radiographic assessment
- Time to progression (TTP): TTP is measured from the date of informed consent to radiographically documented progression according to RECIST 1.1. Participants death and without disease progression, alive without disease progression, or lost to follow-up will be censored at the date of their last radiographic assessment
- Overall survival (OS): OS is measured from date of informed consent to the date of death from any cause. Participants alive or lost to follow-up will be censored at the date of their last radiographic assessment

Survival rate at 12 months and 24 months: The percentage of study population who are still alive for 12 months and 24 months from the date of study enrollment. Participants alive or lost to follow-up will be censored at the date of their last radiographic assessment

Duration of response (DOR): DOR is the time from documentation of tumor response to radiographically documented disease progression

- ORR, TTP, and PFS of the same definitions as above are measured against immune-related RECIST (irRECIST) criteria as one of the secondary endpoints.
- Safety outcome measures: Incidence, nature, and severity of adverse events graded according to the National Cancer Institute Common Terminology Criteria for Adverse Events (NCI-CTCAE v.4)
- Pre-treatment, serial post-treatment plasma EBV-DNA levels, and dynamics of

EBV DNA levels will be measured

- Disease control rate (DCR): The percentage of patients with a CR, PR, or SD  $\geq$  6 months per RECIST 1.1
- Time to response (TTR): TTR is measured from the date of informed consent to first radiographically documented tumor response per RECIST 1.1
- Quality of life (QoL): as assessed by the European Organization for Research and Treatment of Cancer Core Quality of Life Questionnaire (EORTC-QLQ-C30) and the head and neck cancer-specific H&N-35 questionnaires

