#### **6.6.5 Assessment of Causality of Adverse Events**

Investigator(s) should use their knowledge of the patient, the circumstances surrounding the event, and an evaluation of any potential alternative causes to determine whether an adverse event is considered to be related to the study drug, indicating “Yes” or “No” accordingly. The following guidance should be taken into consideration:

- Temporal relationship of event onset to the initiation of study drug
- Course of the event, with special consideration of the effects of dose reduction, discontinuation of study drug, or reintroduction of study drug (as applicable)
- Known association of the event with the study drug or with similar treatments
- Known association of the event with the disease under study
- Presence of risk factors in the patient or use of concomitant medications known to increase the occurrence of the event
- Presence of non-treatment-related factors that are known to be associated with the occurrence of the event

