### **7.3 Early Stopping Rule**

Excessive toxicity will also be monitored. Assuming no more than a 10% SAE rate on historical treatment, the increase of treatment-related SAE to a rate of 30% or greater in the studied treatment will be considered unacceptable, and the study will be then stopped prematurely and will early stop the trial if treatment related SAE >30%. Upon the recruitment of these 38 patients, if 10 or more patients had treatment-related SAE, the study will be stopped. The corresponding lower bound of exact one-sided 90% confidence interval is 30.5%.

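### Section 6.3 labels almost every unexplained death a nasopharyngeal cancer death, which skews the cause-of-death table and is not reconciled with the relatedness assessment

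*Protocol*

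**What the plan says.** Section 6.3 of the protocol first requires that "All causes of death (if occur) will be recorded". It then adds a default: "Deaths due to unknown cause are counted as deaths due to NPC if disease is still present at last assessment". The default has no time window, does not mention the last infusion, and does not refer to the causality sections.

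The other relevant places are these:

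- **Section 3.1** makes "Measurable disease according to the RECIST criteria (version 1.1) for the evaluation of measurable disease" an entry condition. Section 3.2 excludes disease that could be treated locally with curative intent.
- **Section 6.2** states that "OS is measured from date of informed consent to the date of death from any cause". PFS likewise counts any death. TTP censors deaths without progression, whatever their cause.
- **Section 6.6.5** asks the investigator for a yes/no judgement resting on, among other things, "an evaluation of any potential alternative causes to determine whether an adverse event is considered to be related to the study drug". Section 6.6.6 gives the timing of the event relative to the drug the deciding weight and allows two answers, related or not related.
- **Section 7.3** uses that attribution in a decision: "if 10 or more patients had treatment-related SAE, the study will be stopped".

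**The concern.** A cause-of-death rule should separate cases that differ. This one separates almost none. Its condition describes nearly the whole trial population, so an unexplained death shortly after an infusion and one many months later get the same label.

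The label also errs in one direction only. It can move a possible drug death into the disease column and never the reverse. There is no control arm against which an excess of deaths could show, and toxicity and tolerability are a secondary objective (section 2.2). A reader of the final report would see few or no deaths of unknown cause and could take that as evidence that deaths were explained.

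A second problem is that section 6.3 supplies an alternative cause without evidence, while section 6.6.5 asks the investigator to weigh alternative causes and section 6.6.6 puts timing first. The same death could stand as an NPC death in one table and as related to the drug in another. The protocol does not say whether the default may inform the relatedness answer that feeds section 7.3.

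**Working it through.** The plan states no figure that depends on this rule, so there is nothing to reproduce. The check compares passages, with three short calculations to bound what can be said.

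**1. How many patients meet the condition?** Measurable disease is required at entry (3.1), so disease can be absent at the last assessment only after a complete response. The background section on anti-PD-1 therapy reports, for the cited nivolumab study, "A total of 44 patients were evaluated and the overall ORR was 20.5% (CR = 1; PR= 8").

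- Complete responders: 1/44 = 2.3%.
- Patients with disease still present: 43/44 = 97.7%.

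This is a proxy from another drug. If complete responses are more frequent here the share falls, but the condition would still cover most patients.

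**2. Does any efficacy endpoint need the rule?** Going through section 6.2:

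- OS and the 12- and 24-month survival rates depend on whether the patient is alive, not on why a patient died.
- PFS counts progression or any death.
- TTP censors deaths without progression, regardless of cause.
- ORR, DCR, DOR and TTR rest on tumour response or progression.

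None uses cause of death, and no NPC-specific survival endpoint is defined. The rule therefore affects only how deaths are described.

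**3. Does the rule remove deaths from safety data?** Section by section:

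- 6.6.1 defines adverse events without regard to causality.
- 6.6.2 makes a fatal event serious, with no exemption for disease-related deaths.
- 6.6.6 lists a fatal outcome among the recorded outcomes.
- 6.6.5 and 6.6.6 make relatedness a separate judgement by the investigator.

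Nothing in 6.3 overrides these. The gap is that the link between them is unstated.

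**4. How many deaths could be affected?** The background gives 12-month OS of 66.7% (pembrolizumab study) and 59% (nivolumab study). Applied to 38 patients:

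- 38 × (1 − 0.667) = 12.7 deaths
- 38 × (1 − 0.59) = 15.6 deaths

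If those rates carry over, about 13 to 16 patients would die of any cause in the first year, so causes of death will have to be classified often. The protocol gives no information on what share would be unexplained, so these totals are not estimates of affected deaths.

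**5. What if staff let the default override the relatedness judgement?** The protocol does not prescribe this, so what follows is illustration only. Let p be the true treatment-related SAE rate per patient and m the number of patients whose only treatment-related SAE is a death that goes uncounted. The 7.3 threshold is then reached with probability P(X ≥ 10 + m), where X is binomial(38, p).

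| p | m = 0 | m = 1 | m = 2 | m = 3 |
|---|---|---|---|---|
| 0.10 | 0.0034 | 0.0009 | 0.0002 | 0.0000 |
| 0.30 | 0.7449 | 0.6165 | 0.4764 | 0.3413 |

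At the 30% rate that section 7.3 calls unacceptable, each uncounted patient would lower the chance of stopping by about 13 to 14 percentage points (0.7449 − 0.6165 = 0.128; 0.6165 − 0.4764 = 0.140; 0.4764 − 0.3413 = 0.135). This shows why the link to 7.3 should be written down. It does not show that the loss will occur.

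**The case against.** The strongest reply is that section 6.3 only sets a descriptive tally. Adverse events are collected regardless of cause, fatal events are serious, relatedness is judged separately, and section 7.3 counts events by that judgement. One death can carry both a cause-of-death entry and a relatedness entry without contradiction. All of this stands.

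A reader might infer that the rule strikes unexplained deaths from the safety result, or that it flatly contradicts section 6.6.5. The documents support neither: no sentence exempts such deaths from recording or declares them unrelated. The fault is a missing link between the sections.

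A reader might also want to size the problem from the fatal events in the background: one drug-related death in the pembrolizumab study and one suspected in the gastric cancer cohort. That does not work. The first was due to sepsis and the second was suspected to be rupture of a pre-existing aneurysm, so each had a stated or suspected cause and the rule would not have touched it. The lung cancer expansion cohort reported no treatment-related death. A death with an evident cardiac, neurological or bleeding event is also not plainly of unknown cause.

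It is fair to add that section 6.6.6 treats death mainly as an outcome and does not spell out how a death with no identified event is logged. That gap would remain if the sentence in 6.3 were simply deleted.

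Finally, cause-of-death tables are often left to an analysis plan. Here the protocol has already fixed the rule, so the correction belongs in the protocol.

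**Conclusion.** The point holds in a limited form. Section 6.3 in practice codes an unknown cause as NPC for everyone except complete responders, without regard to time since the last dose. It serves no efficacy endpoint, biases the reported cause-of-death table away from possible drug-related deaths, and is not reconciled with sections 6.6.5, 6.6.6 and 7.3.

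The near-universal reach of the condition follows from the entry criteria; the figure of about 98% also assumes a complete response rate like that in the nivolumab study. The direction of the bias follows from the rule itself. Its size cannot be estimated, because nothing in the protocol says how many deaths would be unexplained. No stated figure, endpoint or error rate changes. Any effect on the 7.3 count depends on staff carrying the default over into the relatedness judgement, which the protocol neither prescribes nor rules out.

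**What to change.** Replace the default sentence in section 6.3 with three statements:

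- Deaths of unknown cause are recorded and reported as their own category, each with the number of days since the last dose.
- Each such death is assessed for relatedness under section 6.6.5.
- That assessment, and no default to NPC, determines whether the death enters the section 7.3 count.

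Add to section 6.6.6 how a death with no identified event is entered on the case report form, so that it reaches the assessment.

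A listing that treats deaths of unknown cause soon after the last dose as possibly related can be added as a sensitivity analysis, with its window fixed in advance. It should not become the rule for the 7.3 count. That would be the opposite default, would equally bypass section 6.6.5, and would change the behaviour of the stopping rule without that behaviour having been worked out.

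The cost is a few sentences in a protocol amendment, with no extra patients and no change to any endpoint. The number of deaths attributed to disease becomes slightly smaller, and the safety report gains an unknown category.

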### **6.4 Criteria for Removal from Protocol Treatment**

- Disease progression
- Inter-current disease that would affect assessments of clinical status to a significant degree, require discontinuation of drug, or both.
- Unacceptable toxicity.
- The patient may withdraw from treatment at any time for any reason. The reason should be recorded. Follow-up will be continued for all consenting patients for up to 2 years.

### **6.5 Exploratory Biomarkers**

- Archived NPC tissues will be retrieved from various pathology laboratory in Hong Kong in FFPE slides
- For blood-based biomarkers, the logistics will be as follows,
  - Peripheral blood will be collected in lithium heparin tubes every 2 weeks for 8 weeks.
  - Extracellular Vesicle (EV) Isolation
    - Plasma will be extracted using low-speed centrifugation and cryopreserved for further analysis using standard protocols. Extracellular vesicles will be isolated and purified from cryopreserved plasma using ExoQuick® ULTRA EV Isolation Kit for Serum and Plasma or other commercially available kits. Purified EV will be obtained according to the kit manufacturer's instructions.

- Nanoparticle Tracking Analysis (NTA) and Total Protein Isolation of EV
  - EV characterisation will be performed by NTA provided by NanoSight NS300 or other commercially available tools. Total protein will be isolated from purified EV using Total Exosome RNA & Protein Isolation Kit (Invitrogen™) or other commercially available kits and obtained according to the kit manufacturer's instructions. Protein qualitative detection will be performed by western blot.
- Flow Cytometry of Total Protein from EV
  - Total protein will be labelled with antibodies directed against CD4, CD8, CD3, CD16, CD25, CD45RA, CD56, CD62L, CD-83, CD127, ICOS, PD-1, PD-L1, CTLA-4, FoxP3, TIM-3, Ki67 and other proteins of interest. Antibodies will be purchased from BD Bioscience, BioLegend, eBioscience, or Beckman Coulter. Permeabilization will be performed using FOXP3 Fixation/Permeabilization Concentrate and Diluent kit (eBioscience™) or other commercially available kits. Proteins will be interrogated by LSR II flow cytometer (BD) and results will be analysed using FlowJo software (Tree Star).
- Prognostic and predictive power of exploratory bio-markers will be explored
  - Expression level of PD-L1 levels in archived NPC tissues
  - Pre-treatment and post-treatment levels of TGF $\beta$ 1
  - Pre-treatment and post-treatment plasma exosomal PD-L1 levels

## 6.6 Safety Reporting

### 6.6.1 Adverse Events

- According to the ICH guideline for Good Clinical Practice, an adverse event is any untoward medical occurrence in a clinical investigation subject administered a pharmaceutical product, regardless of causal attribution. An adverse event can therefore be any of the following:
- Any unfavorable and unintended sign (including an abnormal laboratory finding), symptom, or disease temporally associated with the use of a medicinal product, whether or not considered related to the medicinal product
- Any new disease or exacerbation of an existing disease (a worsening in the character, frequency, or severity of a known condition)
- Recurrence of an intermittent medical condition (e.g., headache) not present at baseline
- Any deterioration in a laboratory value or other clinical test (e.g., ECG, X-ray) that is associated with symptoms or leads to a change in study treatment or concomitant treatment or discontinuation from study drug

- Adverse events that are related to a protocol-mandated intervention, including those that occur prior to assignment of study treatment (e.g., screening invasive procedures such as biopsies)

### **6.6.2 Serious Adverse Events (SAE)**

- A serious adverse event is any adverse event that meets any of the following criteria:
  - Is fatal (i.e., the adverse event actually causes or leads to death)
  - Is life threatening (i.e., the adverse event, in the view of the Investigator(s), places the patient at immediate risk of death)
  - This does not include any adverse event that, had it occurred in a more severe form or was allowed to continue, might have caused death.
  - Requires or prolongs inpatient hospitalization
  - Results in persistent or significant disability/incapacity (i.e., the adverse event results in substantial disruption of the patient's ability to conduct normal life functions)
  - Is a congenital anomaly/birth defect in a neonate/infant born to a mother exposed to study drug
  - Is a significant medical event in the Investigator(s)'s judgment (e.g., may jeopardize the patient or may require medical/surgical intervention to prevent one of the outcomes listed above)
- The terms “severe” and “serious” are not synonymous. Severity refers to the intensity of an adverse event (e.g., rated as mild, moderate, or severe, or according to National Cancer Institute Common Terminology Criteria for Adverse Events [NCI-CTCAE]; the event itself may be of relatively minor medical significance (such as severe headache without any further findings).
- Severity and seriousness need to be independently assessed for each adverse event recorded in the clinical database.

### **6.6.3 Adverse Events of Special Interest (AESI)**

- AESIs are a subset of Events to Monitor of scientific and medical interest specific to the Merck Drugs in this protocol. Such an event might require further investigation in order to characterize and understand it.
- AESIs include following:
  - Infusion-related reactions including immediate hypersensitivity.
  - Immune-related adverse events.
  - TGF- $\beta$  inhibition mediated skin reactions.
  - Anemia.
  - Bleeding AEs.
- Any AE that is suspicious to be an AESI do not require expedited reporting unless they are serious. Should the AESI be serious, a SAE form should be filled instead and the reporting process for SAEs should be followed.

#### **6.6.4 Pregnancy Reports**

- Female patients of childbearing potential will be instructed to immediately inform the Investigator(s) if they become pregnant during the study.

#### **6.6.5 Assessment of Causality of Adverse Events**

Investigator(s) should use their knowledge of the patient, the circumstances surrounding the event, and an evaluation of any potential alternative causes to determine whether an adverse event is considered to be related to the study drug, indicating “Yes” or “No” accordingly. The following guidance should be taken into consideration:

- Temporal relationship of event onset to the initiation of study drug
- Course of the event, with special consideration of the effects of dose reduction, discontinuation of study drug, or reintroduction of study drug (as applicable)
- Known association of the event with the study drug or with similar treatments
- Known association of the event with the disease under study
- Presence of risk factors in the patient or use of concomitant medications known to increase the occurrence of the event
- Presence of non-treatment-related factors that are known to be associated with the occurrence of the event

#### **6.6.6 Methods of Recording Adverse Events**

- All AEs must be documented in the appropriate section of the CRF. An SAE report form (initial or follow up) must be completed in case of any of the seriousness criteria is met.
- The following aspects must be recorded for each event in the CRF:
  - A description of the AE in medical terms, not as reported by the subject;
  - The date of onset (start date)
  - The time of onset (start time)
  - The date of recovery (stop date)
  - The time of recovery (stop time)
  - The severity of the sign and/or symptom or clinically significant abnormal laboratory
  - Value according to NCI-CTCAE v.4. If no toxicity grade is described for a given sign, symptom or abnormal laboratory value, the Investigator(s) will grade the severity as mid (grade 1), moderate (grade 2), severe (grade 3), or life-threatening or disabling (grade 4).
  - Death (grade 5) as defined by NCI-CTCAE v.4 is mainly regarded as an outcome and will be documented accordingly (see below).
- The causal relationship to binrafusp alfa as assessed by the Investigator(s); the decisive factor in the documentation is the temporal relation between the AE and the study drug. The following judgments of the causality to study drug or study procedures are to be used:
  - Not Related = not suspected to be reasonably related to the

investigational product. AE could not medically (pharmacologically/ clinically) be attributed to the investigational product under study in this protocol

- Related = suspected to be reasonably related to the investigational product. AE could medically (pharmacologically/ clinically) be attributed to the investigational product under study in this protocol
- Action taken on binrafusp alfa (none, medication discontinued, dose reduction, medication delayed, reduction of infusion rate).
- Other action (none, concomitant medication given, new or prolonged hospitalization, procedural surgery).
- The outcome according to the following definitions:
  - Recovered without sequelae (AE disappeared)
  - Recovered with sequelae (AE has resulted in permanent disability/incapacity)
  - Not yet recovered
  - Not recovered at death
  - Change in toxicity grade/severity or seriousness (e.g., an AE with no change of toxicity grade but newly classified as an SAE due to hospitalization.
  - Fatal (AE resulted in death)
- Concomitant medication given: Yes or No (Note: If this question is answered “Yes” the corresponding serious criteria must be ticked) § Subject died
  - Life-threatening
  - New or prolonged hospitalization
  - Persistent/significant disability § Congenital abnormality
  - Important medical event
  - Seriousness: Yes or No
- If in any one patient the same AE occurs on several occasions, then the AE in question must be documented and assessed anew each time.

